4.6 Data Collection

Patients approached by study staff that agrees to participation will be captured in the remote data capture system (REDCap⁴⁵). Potential eligible patients found to be ineligible or eligible but decline participation will be captured in a recruitment tracking log. The reason for ineligibility or reason for decline will be captured along with patients' age, sex, and race/ethnicity.

Self-reported responses from patients and clinicians will be collected at the end of the clinical encounter. At the time of their enrollment clinicians will complete a survey that collects data on their demographics. The post baseline survey will be given to the patient and clinician to complete at the clinic at the end of the encounter by the study coordinator or site appointed staff. Patients may be given the option to fill out part of the survey, prior to their visit if time allows. If a patient requests a return envelope, one will be provided to return the survey by mail. If the survey is not received in the 10 days post encounter a

reminder will be mailed to them with a copy of the survey along with a return envelope. A courtesy call will be made within 5 days post the mailing. Every effort will be made to complete the survey at the clinic immediately post encounter as this is the best chance for complete data collection. Another option for patients will be to have a follow up phone call approximately 1-2 days after their clinical encounter, to remind the patient to send their survey back or they will be given the option to complete their survey over the phone at that time.

Data from the medical record will be abstracted for all enrolled patients to capture demographic, clinical and medication prescription data. The time frame for collection will be from prior to enrollment to 12 months post enrollment. For patients that do not have any encounters at the institution for the past 12 months, a scan will be conducted up to 6 months after the 12-month timeline to verify continuity of care at the institution, change in contact information and/or survival status. If no records are available at that time, we will call the patient (number of attempts as authorized by each IRB), followed by a postal survey if nonresponse persist.

Data to be collected on patients include variables necessary to estimate the risk of stroke and bleeding, age, gender, BMI, smoking status, alcohol consumption, marital status, annual income of household, highest level of education, residency (nursing home), location of primary healthcare and total number of medications patients is currently taking. To further characterize the patients, we will use Chew et al single-item health literacy screener,⁴⁶ a 4-item modified Subjective Numeracy Scale,^{47, 48} and a single-item health status measure.⁴⁹

We will collect information on past use of anticoagulants through medical record review. We will categorize the patients into two cohorts for descriptive and analytical purposes. For patients who are not using an anticoagulant at the time of trial participation will form the 'Start' cohort. They may have used anticoagulation and discontinued >6 months ago, never used anticoagulation, or are using aspirin only. Patients that began an anticoagulant

within the past 10 days of the enrolled encounter that were prescribed an anticoagulant within the emergency department or an inpatient visit will still be considered a new ‘Start’.

Patients who are on warfarin or NOACs or used them in the past 6 months will form the ‘Review’ cohort. This cohort may include patients who have difficulty maintaining a therapeutic INR, or patients considering switching to a different anticoagulant or to stay on warfarin but switch to home INR monitoring.

The post consent survey for clinicians will collect demographic data (age, gender, specialty, % of their practice dedicated to anticoagulation care).

Calendar of Events

	Prior to Study Enrollment	Prior to Encounter		Post Encounter	12 months Post Enrollment
Patient Completed Forms			R A N D O M I Z E D A T I O N		
Informed Consent	X				
Pharmacy Consent	X				
Survey				X	
Phone ¹					X
Clinician Completed Forms					
Informed Consent	X				
Survey		X		X	
Clinical Data Abstracted from EMR					
Bleeds					X
Strokes					X
INR Tests (# and values outside of 2-3 range)					X
Anticoagulation Prescription		X		X	X
Pharmacist Request					
Anticoagulation					X ²

Use					
-----	--	--	--	--	--

- 1- Patients who do not have utilization within enrolling healthcare system will be contacted via phone for verification of safety data (strokes and bleeds). If no information in the record and follow-up is necessary we will call patients the maximum number allowed by the IRB followed by a postal survey
- 2- Pharmacist records will be requested for 12 months prior to enrollment through 10 months post enrollment.

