1.0 Aims

The goal of this study is to determine the extent to which standard care plus the Anticoagulation Choice tool promotes shared decision making (SDM) and impacts anticoagulation uptake and adherence versus standard care without this tool in patients with nonvalvular atrial fibrillation (AF).

Aim 1. To what extent does use of the ANTICOAGULATION CHOICE tool promote high-quality SDM versus standard care?

Using encounter video recordings and post-visit patient and clinician questionnaires, we will assess **SDM quality** (primary endpoint) **and processes**.

We hypothesize that use of the tool will improve SDM irrespective of patient literacy/numeracy, stroke risk, anticoagulation use at baseline, or type of clinic.

Aim 2. To describe the impact Anticoagulation Choice tool has on the rate of anticoagulation, the choice of anticoagulant, and adherence to anticoagulation in at-risk patients with AF versus the impact of standard care.

Using medical records and pharmacy profiles, we will determine the choice of anticoagulation, changes in anticoagulant use over time, and 12-month drug persistence, in all patients and in subgroups defined by patient literacy/numeracy, stroke risk, anticoagulation use at baseline, and type of clinic. As safety outcomes, we will monitor serious bleeding or strokes requiring medical attention.

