4.9 Statistical Analysis

4.9.1 Analysis Plan

The study will be analyzed according to the *intention to treat principle (ITT)*, including all patients enrolled to the study in the arm to which they were assigned, regardless of which they were assigned to (e.g., standard care or Anticoagulation Choice + Standard Care). Reporting will include 'Per Protocol', complete data for each arm plus the ITT analysis where imputation analysis methods will be utilized to address any missing values (see section 4.9.1.1 for details on missing data analysis). Baseline characteristics will be reported in the study results with continuous values being reported as means and standard deviations and categorical values reported as counts and frequencies and compared between study arms using t-tests and chi-squared tests. Any baseline imbalances ($p < 0.05$) will be explored as a possible factor to adjust for when the outcome measures are

analyzed. We will adhere to the CONSORT guidelines to transparently report study results and ensure that sufficient information is included to allow for assessment of the study's internal and external validity.

We will use standard techniques appropriate for trials, with each outcome compared between study arms using t-tests for continuous outcomes and chi-square tests for dichotomous outcomes. If there are differences in baseline characteristics found by statistical means or found to have clinical relevance between the two study groups, these will be accounted for using regression models which include an indicator for study arm.

We will perform descriptive analyses to describe any potential heterogeneity of treatment effect (HTE) and facilitate synthesis of subgroup results in future meta-analyses. We will conduct descriptive HTE analyses by clinic (academic, community and safety net), by cohort (start or review cohort), by stroke risk (CHA₂DS₂-VASc score of 1 or ≥ 2 for men and 2 or ≥ 3 for women), and by numeracy (Less than adequate vs. not). The outcomes assessed with HTE analyses will be the same as those assessed in the trial (e.g., SDM and communication quality, knowledge, and decisional satisfaction).

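### Self-rated numeracy and literacy define subgroups, but the plan does not ensure that they are recorded before randomisation or before exposure to the tool

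*Combined protocol and SAP*

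**What the plan says.** Literacy and numeracy have a stated role in both aims. Under Aim 1 the hypothesis is that "use of the tool will improve SDM irrespective of patient literacy/numeracy", along with other factors. Under Aim 2, anticoagulant choice and persistence are to be examined "in subgroups defined by patient literacy/numeracy, stroke risk, anticoagulation use at baseline, and type of clinic". Section 4.9.1 then lists the factors for the heterogeneity analyses, which it calls descriptive: clinic, cohort, stroke risk, and "by numeracy (Less than adequate vs. not". Literacy is not in that list.

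The instruments, in section 4.6, are a "single-item health literacy screener" and "a 4-item modified Subjective Numeracy Scale". They are introduced among variables that characterise the patients, with no statement of when they are completed.

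On timing, section 4.6 places patient self-report at the end of the encounter, and allows the survey to come back by mail or be completed by phone. It adds: "Patients may be given the option to fill out part of the survey, prior to their visit if time allows". The Calendar of Events marks the patient survey once, under Post Encounter, to the right of the randomisation column. Clinicians have a survey both before and after the encounter.

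**The concern.** A subgroup contrast keeps the protection of randomisation only if membership is fixed before the arms diverge. Clinic, cohort and stroke risk meet that condition because section 4.9.3 makes them stratification factors. Numeracy and literacy are not strata, and no other baseline measurement of them is described.

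The numeracy scale is self-rated. Section 3.0 describes a tool that shows personal risk in words, in numbers and in a 100-person pictograph. A patient who has just worked through that display might rate his or her comfort with numbers differently, and this could happen in one arm only. Patients classed as low-numeracy in the tool arm would then no longer be the counterparts of those so classed under standard care. Because pre-visit completion is optional, the time of classification may also differ between patients within an arm.

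At stake is the reading of the Aim 1 claim that the tool works whatever the patient's literacy or numeracy, and of the matching Aim 2 subgroups.

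**Working it through.** **Placement of the items.** The plan states no figure that could be reproduced here, so the first step sets the text side by side.

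1. The two scales are self-report (section 4.6).
2. Patient self-report is collected at the end of the encounter (section 4.6).
3. Only one patient survey is scheduled, and it is post-encounter (Calendar of Events).
4. An unspecified part may be done earlier, if there is time (section 4.6).

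It follows that, with the plan carried out as written, the five items can be answered after exposure. That they sit in this survey is an inference; no sentence says so.

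**How large could the effect be?** This is an illustration. The knowledge-score SD of 18 comes from the table in section 4.9.2. The share with low numeracy, the gap between subgroups, the share moved and the correlations are assumptions. The true effect is taken to be equal in both subgroups. In the tool arm only, a fraction m of low-numeracy patients is reclassified as adequate.

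*Case A: those who move are average low-numeracy patients.* Let p be the true low-numeracy share and g the gap in mean knowledge between the subgroups. The effect in the low subgroup is unbiased. The effect in the adequate subgroup is too small by g × pm / (1 − p + pm), which is also the spurious difference between subgroups.

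- p = 0.5, g = 9, m = 0.10: 9 × 0.05/0.55 = 0.8 points
- p = 0.5, g = 9, m = 0.20: 9 × 0.10/0.60 = 1.5 points
- smallest in the range (p = 0.3, g = 9, m = 0.05): 9 × 0.015/0.715 = 0.2 points
- largest in the range (p = 0.5, g = 18, m = 0.30): 18 × 0.15/0.65 = 4.2 points

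*Case B: those who move sit just below the cut.* Take latent numeracy as standard normal with p = 0.5 and correlation r with knowledge. Let c be the normal quantile of 0.5(1 − m) and φ the normal density. The bias is 18r × [φ(0)/0.5 − φ(c)/(0.5(1 − m))] in the low subgroup and 18r × [φ(c)/(1 − 0.5(1 − m)) − φ(0)/0.5] in the adequate subgroup.

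- m = 0.10: c = −0.126, φ(c) = 0.396. The brackets are −0.082 and −0.078. For r = 0.3 to 0.5 the bias is −0.4 to −0.7 points in each subgroup.
- m = 0.20: c = −0.253, φ(c) = 0.386. The brackets are −0.168 and −0.154. The bias is −0.8 to −1.5 points.

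Both subgroup effects shrink, but the spurious difference between them stays below 0.2 points. With m = 0, as pre-randomisation measurement ensures, there is no bias in either case.

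**Scale.** With 999 patients, equal arms and p = 0.5, each subgroup has about 250 per arm. The standard error of a subgroup effect is 18 × √(2/250) = 1.6, and that of the difference between two subgroup effects is 18 × √(4/250) = 2.3. Every Case B bias is under one standard error. Case A exceeds one only with a wide gap and many movers.

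**Link to the main analysis.** Section 4.9.1 lets a baseline imbalance at p < 0.05 lead to adjustment. Suppose post-encounter numeracy were tabulated as a baseline characteristic. With p = 0.5 and about 499.5 per arm, m = 0.10 gives 50% against 45% low, an expected z of 0.05/0.0316 = 1.6. With m = 0.20 it is 50% against 40%, an expected z of 0.10/0.0315 = 3.2. The larger shift would probably trigger adjustment for a variable that the tool itself had changed.

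**The case against.** The strongest reply is that the plan already goes most of the way. Decisional conflict, satisfaction and the report of the decision made cannot be answered before the visit, so items on patient characteristics are the natural content of the pre-visit part. That is plausible, and the team may intend it. But the plan neither names those items nor requires pre-visit completion, so the gap remains.

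Second, no mechanism is shown. The documents do not reproduce the scale items, and give no evidence that one visit changes self-rated numeracy or in which direction. For literacy there is not even a suggested route, and it appears in the Aims but not in the list in section 4.9.1. This stands: the point is that membership can be affected, not that it is.

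Third, the heterogeneity analyses are descriptive, and if the borderline patients are the ones who move, a claim of similar benefit across numeracy levels is hardly disturbed. This also stands, and limits the consequence.

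A reader might go further and infer that the numeracy results are biased by a material amount, for example by setting an assumed shift against the 5.6-point detectable difference in section 4.9.2. The documents do not support that. Any shift is assumed, and 5.6 points belongs to a sample of 333, not to a numeracy subgroup whose size the plan does not give.

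**Conclusion.** The point holds as a minor and inexpensive improvement. As written, the plan does not guarantee that numeracy and literacy are pre-randomisation variables, although the Aims use both as subgroups and section 4.9.1 uses numeracy. This rests on the inference that the items belong to the single scheduled patient survey.

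The size of any bias is unknown. Over the assumed ranges above, the spurious difference between subgroups on the knowledge score lies between near 0 and 4.2 points, and the upper end needs unfavourable assumptions throughout.

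A reader might also infer that the primary comparison is compromised. It is not: the arms remain as randomised. It would be touched only if post-encounter values were treated as baseline and used for adjustment under section 4.9.1.

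**What to change.** Amend section 4.6 and the Calendar of Events so that every patient completes the one literacy and four numeracy items after consent and before randomisation. Completion merely before the encounter is weaker, because section 4.3 randomises after consent and the allocation could already be known.

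For patients already enrolled, where the time of completion is known:

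- label classifications made after the encounter as post-exposure;
- repeat the numeracy and literacy subgroup analyses in those who completed the items before the visit, as a sensitivity analysis;
- do not use post-encounter values as baseline adjustment covariates.

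The cost is five short items, a minute or two before the visit. Consent and randomisation already precede the encounter, and section 4.2.3 describes patients at the Mayo Clinic site being approached in person before their appointment, so no new contact is needed. The sensitivity analysis can be run only where completion times were recorded.

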4.7 Outcome Measures

4.7.1 SDM quality

SDM quality will measure (a) knowledge transfer; (b) concordance; (c) quality of communication and satisfaction with shared decision making; and (d) satisfaction with the decision-making process.

Knowledge transfer is 6 questions about AF and anticoagulation. The 6 questions use a response format “true / false / do not know”, and are answered with full access to the decision aids since they are not meant to test recall. Correct responses will be summed and divided by the total number of questions asked. If a patient answers at least 1 knowledge question then they will be assessed for this outcome, where all missing responses will be coded as incorrect.

Knowledge of risk will contain one question that asks patients to estimate their own risk of stroke. Correct answers will be within $\pm 10\%$ (strict score) and $\pm 30\%$ (liberal score) *relative* to the calculated risk estimate.

Collaborative agreement will assess decision concordance between the patient and the clinician. Both the patient and clinician will be asked to report about what decision (anticoagulation no/yes-which one) was made during the index visit. Agreement will be calculated between both parties and reported.

Patient decision satisfaction will be assessed using the Decisional Conflict Scale (DCS).⁵⁰

⁵¹ The 16 items of DCS are scored on a 0-4 scale; the items are summed, divided by 16 and

then multiplied by 25. The scale is from 0-100 where higher scores are reflective of uncertainty about the choice. There are 5 DCS subscales, where a DCS subscale consists of 3 questions (1 subscale of 4). If 2 of 3 (or 3 of the 4) questions within a subscale have responses, then the patient would be considered as a responder and a score could be calculated. If more than one response per subscale is missing then that specific subscale is not calculated for the patient. An overall DCS score can be calculated if no more than 5 responses are missing as long as each missing response falls into a different subscale.

Quality of Communication will be assessed with a modified version of three questions from the CAHPS Clinician and Group survey⁵². CAHPS surveys include questions to assess patient perspectives of communication with their clinician. These questions indicate the extent to which the communication is patient-centered. Three questions ask about specific aspects of technical (explain things in a way you could understand) and affective (show respect for what you have to say) communication. Each item is assessed on a 3 point scale (Yes, definitely; Yes, somewhat and No) that will be individually reported, no composite score will be done. Three modifications are made to improve the relevance of the items to the present study: (1) Instructions were changed from “These questions ask about your most recent visit with this doctor. Please answer only for your own health care.” to “Thinking of the conversation you just had with your clinician about blood thinners (anticoagulation medications), please select the most appropriate response to each item below.” (2) “During your most recent visit” was removed from the item stems. (3) “This doctor” was replaced with “this clinician.”

Patient satisfaction with encounter will be assessed with 1 question on a 7 point likert scale. Patients will be asked whether they would recommend the approach used to others for other discussions.

Clinician satisfaction with encounter will be assessed with 2 questions. A 5 point likert scale questioning satisfaction with discussion about anticoagulation medication choice. The clinician will also be asked whether they would recommend the approach used to other clinicians for other discussions on a 7 point Likert scale.

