4.9.1.1 Missing Data

We will make every effort to minimize missing data. Trial enrollment and the fidelity of follow-up procedures will be reviewed during bi-weekly conference calls. A study biostatistician will conduct frequency reports to assess for missing data, and the study team, which is experienced in conducting multicenter trials, will trouble shoot any problems encountered. We will report rates of missing data for each outcome by study arm and send missing data reports to sites.

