4.9.2 Sample Size Estimation

*The table shows the detectable effect for each of the outcomes of interest if we were to have data on that outcome from a total of 333 patients (1% of available population). This provides enough power ($\alpha=0.05$; two-sided difference) to detect meaningful differences across arms for all SDM quality and process outcomes. Our intent, however, is to have enough power to detect important differences when we conduct analyses of groups or cohorts of patients. Most of these analyses will divide the participants into 2 cohorts (e.g., start and review cohorts), except for the subgroup analysis by clinic, which divides the total sample into 3 cohorts: academic, community, and safety net clinic. That is the only analysis with three groups. Given this, we would need 3 times the sample size listed in the table, or **999 participants (3% of available sample)** to address all planned subgroup analyses. These are minimum targets for recruitment and we do not plan to limit recruitment in any way to enroll up*

to this number of patients. It assumes even distribution of participants per subgroup (e.g., start vs. review cohort); since the only grouping with three levels is clinic, each clinic will be expected to recruit similar numbers. Thus, for the main analysis and for other subgroup analyses (n=2 levels),

Outcome (n = 333)	Rate (%) or SD	Detectable effect	Power*
Patient level – SDM quality			
Knowledge transfer [^]	18	5.6	84%
Knowledge of risk	55%	15%	81%
Decisional conflict scale [^]	17	5.2	80%
Clinician level			
Satisfaction [^]	54%	15%	80%
Encounter level – SDM process			
Engagement (OPTION12) [^]	12.6	3.9	80%

[^] Values from iADAPT SDM tool trial; * $\alpha=0.05$; two-sided

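### Does the plan need a new scoring rule for incomplete Decisional Conflict Scale forms?

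*Combined protocol and SAP*

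**What the plan says.** Section 4.7.1 describes the DCS as 16 items scored 0 to 4. For the total, "the items are summed, divided by 16 and" the result is multiplied by 25. It adds: "The scale is from 0-100 where higher scores are reflective of uncertainty about the choice".

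There are five subscales, four with three items and one with four. A patient counts as a responder on a subscale "If 2 of 3 (or 3 of the 4) questions within a subscale have responses". An overall score is allowed "if no more than 5 responses are missing as long as each missing response falls into a different subscale". An accepted form therefore has between 11 and 16 answers.

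For the knowledge score, the same section does say what a blank means: a patient who answers at least one question is scored, "where all missing responses will be coded as incorrect".

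Section 4.9.1 describes an intention-to-treat analysis "where imputation analysis methods will be utilized to address any missing values" and refers to 4.9.1.1 for the details. Section 4.9.1.1 covers prevention and reporting ("We will report rates of missing data for each outcome by study arm") and names no imputation method.

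The table in 4.9.2 has one DCS row: SD 17, detectable effect 5.2, power 80%, 333 patients in total.

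**The concern.** The plan says when an incomplete DCS form may be scored but not how. The only written divisor is 16. If an analyst sums the answers present and still divides by 16, each blank acts as a zero, the answer showing least conflict. A patient who skips items then looks more settled than a patient with the same attitude who answers everything, and the form can no longer reach 100. For subscales there is no formula at all, even for complete forms.

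The DCS is one of the measures of SDM quality, which section 1.0 (Aim 1) names as the primary endpoint. If the literal reading were used and skipping were common, the treatment difference would shrink. If skipping differed between arms, a small artificial difference could appear. Two analysts following the text could also report different scores for the same patient.

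**Working it through.** **Inputs.** From 4.7.1: 16 items, each 0-4; total = sum / 16 x 25; at most one blank per subscale and five overall. From 4.9.2: SD 17, difference 5.2, 333 patients, two-sided alpha 0.05. The documents give neither skipping rates nor an expected mean DCS, so both are assumed below.

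**1. The plan's own figures.** A complete form has maximum 16 x 4 / 16 x 25 = 100, so the stated range holds. With 166.5 patients per arm, a t-test for 5.2 with SD 17 has power 79.5% (79.7% by the normal approximation), which agrees with the stated 80%.

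**2. One form under the literal reading.** With k blanks the maximum is (16-k) x 4 / 16 x 25. The score is (16-k)/16 times the score based on the answered items.

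| Blanks k | Maximum | A form scoring 30 on its answered items becomes |
|---|---|---|
| 1 | 93.75 | 30 x 15/16 = 28.1 |
| 2 | 87.5 | 30 x 14/16 = 26.25 |
| 3 | 81.25 | 30 x 13/16 = 24.4 |
| 4 | 75 | 30 x 12/16 = 22.5 |
| 5 | 68.75 | 30 x 11/16 = 20.6 |

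These are effects on single forms, not shifts in arm means.

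**3. The sensible readings compared.** Take a form with one blank in every subscale and answers 4,4 / 2,2 / 1,1 / 0,0 / 3,3,3. The sum is 23 over 11 answers.

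- Divide by the number answered: 23/11 x 25 = 52.3.
- Fill each blank with its subscale mean: (12 + 6 + 3 + 0 + 12)/16 x 25 = 51.6.
- Average the five subscale means: (4 + 2 + 1 + 0 + 3)/5 x 25 = 50.0.
- Literal divisor of 16: 23/16 x 25 = 35.9.

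The form has the most blanks the plan allows and very uneven answers. Even so, the three readings that use the answered items lie within 2.3 points of each other. Only the literal one stands apart.

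**4. Arm comparison, equal skipping, literal reading.** Suppose a share p of forms in each arm has k blanks. The mean difference becomes 5.2 x (1 - p x k/16). The SD is recomputed in each arm from the mixture, with control mean 20, 30 or 40 and the intervention mean 5.2 lower. The test is a two-sided t-test with 1:1 allocation and no clustering.

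| p | k | Difference | Power, n=333 | Power, n=999 |
|---|---|---|---|---|
| 0 | 0 | 5.20 | 79.5% | 99.8% |
| 5% | 1 | 5.18 | 79.4% | 99.8% |
| 10% | 2 | 5.135 | 79.1-79.4% | 99.8% |
| 20% | 1 | 5.135 | 79.3-79.4% | 99.8% |
| 20% | 2 | 5.07 | 78.9-79.3% | 99.8% |
| 20% | 5 (extreme) | 4.875 | 75.4-78.0% | 99.6-99.7% |

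Power moves little because the SD falls along with the difference.

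**5. Unequal skipping, literal reading.** The artificial difference is mean x k/16 x excess share of incomplete forms. At the low end, 20 x 1/16 x 0.05 = 0.06. In the middle, 30 x 2/16 x 0.10 = 0.375. At the high end, 40 x 2/16 x 0.10 = 0.50. All are small beside 5.2.

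**The case for a change.** The strongest case for a change is that the scoring of a measure belonging to the primary endpoint should be fixed before anyone sees the data. The written divisor is 16, the general missing-data section names no method, and the plan is explicit about blanks for the knowledge score but silent for the DCS. One sentence would close the gap at no cost, and an error of about 2 to 9 points on a single form scoring 30 is not trivial beside 5.2.

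What stands is that the text is silent and that a stated rule would be tidier. The rest is weaker. The formula is introduced for the 16 items; it defines the score of a complete form and does not prescribe zero for a blank. A form capped below 100 still lies within 0-100, so the range and the formula do not contradict each other. Requiring two of three (or three of four) answers in a subscale makes sense if the score is built from those answers. Where the authors want a blank to count as a particular value, as with knowledge, they say so.

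The subscale point has no visible consequence: 4.9.1 names no subscale comparison and 4.9.2 has only the overall DCS row. The lack of a named imputation method in 4.9.1.1 is a wider matter, and DCS item blanks are only one instance of it.

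**Conclusion.** The gap is real but is a missing detail, not a wrong rule. An analyst would score accepted forms from the items answered, by the answered-item divisor or by subscale means, and both fit the text. Complete forms are unaffected by the choice.

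If the least favourable reading were used instead, and 5-20% of forms lacked one or two items in both arms, power at 333 patients would fall by at most 0.6 percentage points (79.5% to 78.9%). In the extreme case, with 20% of forms lacking all five permitted items, it would be 75.4-78.0%. At the planned 999 patients it stays at or above 99.6%. Unequal skipping of 5-10 percentage points would add 0.06 to 0.50 points.

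These figures rest on assumed skipping rates, on assumed mean scores of 20-40, and on skipped items resembling answered ones. Nothing in the documents suggests that skipping will be heavy or will differ by arm. Section 4.6 aims for completion in the clinic with mail and telephone follow-up, and the missing-data rates by arm promised in 4.9.1.1 should help show a problem. No conclusion of the trial is at risk, and no change to the plan is called for.
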